5.3 Research Laboratory Assays

Blood volumes have been summarized in *Appendix A* (Schedule of Events). The Immunological Assays to be performed with these blood specimens have been described in [Section 8 \(Assessment of Immunogenicity\)](#).

The collection of oral crevicular fluid will be performed with a porous foam swab device that is gently rubbed along the gumline until the foam sponge is saturated. The foam swab is then inserted into an extraction tube that is pre-filled with a buffer solution that elutes the antibodies from the foam swab. A dropper tip, attached to the tube and swab, effectively acts as a syringe-like device which simultaneously squeezes the oral fluid-buffer liquid out of the foam and into the collection tube. Antibodies in oral fluid will be measured by the method described in Section 8.

6 STUDY SCHEDULE

6.1 Screening Visit (Day -45 till -2)

After a participant has signed informed consent and has successfully completed the *Comprehension Assessment Tool*, the following will be performed:

- Assignment of study subject identification number
- Complete medical history will be obtained by interview
- Record all concomitant medications taken within 28 days prior to signing the informed consent form
- Measure oral temperature, blood pressure, and pulse.
- Collect height and weight
- A targeted physical examination is to be performed by a licensed study clinician
- A blood volume of 16 mL is to be obtained for screening laboratories, consisting of:
 - Hematology (4 mL, lavender, EDTA tube): total WBC, ANC, Hg, platelets
 - Chemistry (8.5 mL, red, serum separator tube): creatinine, AST, ALT, TBIL, and CRP
 - Serologies (from same 8.5 mL SST tube for chemistry): hepatitis B surface antigen (HBsAg) and hepatitis C virus (HCV) antibody
 - Human immunodeficiency virus (HIV) antibody (3.5 mL, serum separator tube)
 - For women of child-bearing potential: serum β-HCG (to be analyzed from the specimen obtained for chemistry)

6.2 Visit 1 - Enrollment & Vaccination Dose #1 (Day 1)

A participant that satisfies eligibility will be given an appointment for enrollment. The following activities will be completed prior to vaccination:

- interim medical history or concomitant medications
- A targeted physical examination, if indicated based on review of interim medical history
- Measure oral temperature, blood pressure, and pulse
- Final review of all inclusion and exclusion criteria
- A blood volume of 15 mL for the collection of serum, 80 mL for the collection of peripheral blood mononuclear cells (PBMC), and 12.5 mL for safety laboratory assessment, consisting of:
 - Hematology (4 mL, lavender, EDTA tube): total WBC, ANC, Hg, platelets
 - Chemistry (8.5 mL, red, serum separator tube): creatinine, AST, ALT, TBIL, CRP
 - SARS-CoV-2 antibody test (5 mL), to be performed at University of Maryland Pathology Associates (UMPA)
- Collect nasopharyngeal swab for SARS-CoV-2 PCR test, to be performed at University of Maryland Pathology Associates (UMPA)
- For women of child-bearing potential, a urine pregnancy will be performed
- Collect oral fluid (crevicular fluid)
- Confirmation of ongoing informed consent

Enrollment and randomization may be performed after eligibility has been confirmed. Once randomization has been completed, a prospectively assigned unblinded vaccinator and unblinded checker will check the randomization treatment assignment and prepare the masked study product. The injection site will be cleaned with an alcohol swab. The assigned study product will be administered to the deltoid muscle by intramuscular route. The study product administered, the location, and time of administration will be documented on the appropriate source document.

Following receipt of dose #1 of study product, the participant will be directly observed for at least 20 minutes. The PI (or designee) may determine that a participant requires longer on-site observation or clinical assessment, as needed for significant adverse events. Prior to discharge, the participant will be provided with training on the completion of a *Memory Aid*, given a digital thermometer, and provided follow-up visit information and contact phone numbers for study staff.

6.3 Visit 2 Follow Up (Day 2)

The participant will return to clinic to complete the following:

- Review of the *Memory Aid* and retraining on the use of the *Memory Aid*, if necessary
- Any other unsolicited adverse events (AEs) will be recorded
- A blood volume of 3.5 mL for safety laboratory assessment of CRP
- Prior to discharge, a reminder of the date and time for the next visit will be given to the participant

6.4 Visit 3 Follow Up (Day 8 ±1)

The participant will return to clinic to complete the following:

- Interim medical history or concomitant medications
- A targeted physical examination, if indicated based on review of interim medical history
- Collection and review of the *Memory Aid* for reactogenicity information and completion of the corresponding source document.
- Any other unsolicited adverse events (AEs) will be recorded
- A blood volume 12.5 mL for safety laboratory assessment, consisting of:
 - Hematology (4 mL, lavender, EDTA tube): total WBC, ANC, Hg, platelets
 - Chemistries (8.5 mL, red, serum separator tube): creatinine, AST, ALT, TBIL, CRP
- A blood volume of 40 mL for PBMC (for Cohorts B, C, and D only)
- If available, the result from the PCR testing performed on Day 1 will be provided to the participant
- Prior to discharge, a reminder of the date and time for the next visit will be given to the participant

6.5 Visit 4 Follow Up (for Cohorts A-B) or Vaccination Dose #2 (for Cohorts C and D) (Day 29 ±3)

The participant will return to clinic to complete the following, prior to vaccination:

- Interim medical history or concomitant medications

- A targeted physical examination, if indicated based on review of interim medical history
- Collection of any AEs will be recorded
- A blood volume of 20 mL for serum and 80 mL for PBMC
 - 5 mL for a SARS-CoV-2 antibody test, to be performed at University of Maryland Pathology Associates (UMPA)
- Collect nasopharyngeal swab for SARS-CoV-2 PCR test, to be performed at University of Maryland Pathology Associates (UMPA)
- Collect oral fluid (crevicular fluid)
- For women of child-bearing potential, a urine pregnancy will be performed (for Cohort C and D only)
- Confirmation of eligibility for dose #2, if Cohort C and D

For Cohort C and D, the unblinded vaccinator and unblinded checker will administer the appropriate study product and record the procedure on the respective source document. Following receipt of vaccine, the participant will be directly observed for at least 20 minutes and given instructions on the completion of a *Memory Aid*. Prior to discharge, follow-up visit information and contact numbers will be provided.

6.6 Visit 5 Follow Up, only for Cohort C and D (Day 36 ±1)

The participant will return to clinic to complete the following:

- Interim medical history or concomitant medications
- A targeted physical examination, if indicated based on review of interim medical history
- Collection and review of the *Memory Aid* for reactogenicity information and completion of the corresponding source document.
- Any other unsolicited AEs will be recorded
- A blood volume of 40 mL for PBMC
- The result from the PCR testing performed on Vaccination Dose #2 (Day 29) will be provided to the participant
- Prior to discharge, a reminder of the date and time for the next visit will be given to the participant

6.7 Follow Up, Visit 5 for Cohort A-C, Visit 6 for Cohort C and D (Day 57 ±3)

The participant will return to clinic to complete the following:

- Interim medical history or concomitant medications
- A targeted physical examination, if indicated based on review of interim medical history
- Collection of any AEs (for Cohort C and D only) or SAEs will be recorded
- A blood volume of 15 mL for serum and 80 mL for PBMC
- Collect oral fluid (crevicular fluid)

6.8 Final Follow Up, Visit 6 for Cohort A-B (Day 180 ±14), Visit 7 for Cohort C and D (Day 210 ±14)

The participant will return to clinic to complete the following:

- Interim medical history

- A targeted physical examination, if indicated based on review of interim medical history
- Collection of SAEs will be recorded
- A blood volume of 15 mL for serum and up to 80 mL for PBMC
- Collect oral fluid (crevicular fluid)

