2.2 Work flow of the Phase 1 study in U.S. adults

Eligible subjects will be screened, enrolled, and vaccinated at the CVD Outpatient Vaccine Clinic (located on the 4th floor of HSF1) or Pharmaron (located in the UMB BioPark 1 building). After the documentation of informed consent, subjects will be screened for eligibility; eligible subjects will subsequently be enrolled and randomized to a treatment group. On Day 1 (and Day 29, for participants in Cohorts C and D), study product will be administered, in double-blinded fashion, as an intramuscular injection into the deltoid muscle. Following vaccination, there will be a 20-minute post-vaccination observation period. Following each dose of study product, safety and reactogenicity will be measured by a daily oral temperature and solicited AE reporting over the subsequent 7 days (via a 7-day memory aid); unsolicited AE reporting will occur through 28 days following the last dose of vaccine. The occurrence of any SAEs will be recorded through 6 months after the last dose of vaccine (Day 180 or 210, for participants in Cohort C and D).

Subjects in Steps 1-2 (Cohorts A-B) will complete four additional outpatient visits on Days 8, 29, 57, and 180 (final visit). Subjects in Cohorts C and D will complete five additional outpatient visits on Days 8, 29 (second dose of masked study product), 36, 57, and 210 (final visit). The recording of AEs and concomitant medication change information, the performance of a physical exam (if indicated), and the collection of study-specific samples will be performed during these outpatient visits. Clinical safety laboratory tests will be evaluated on Day 8. The final study visit will be for the collection of SAE information (Day 180 or 210).

After the completion of enrollment of each cohort, the safety data through 7-days post-vaccination are to be reviewed by an independent Safety Monitoring Committee (SMC). The SMC must provide approval prior to the enrollment of the subsequent dose-escalating cohort. Immunology data may not be available at the times of these scheduled SMC reviews.

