2.3 Primary Objectives and Outcome Measures

The primary objectives and outcome measure of this study are the following:

1. Safety and Reactogenicity: To assess the frequency and severity of solicited local (i.e., injective site) and systemic (such as fever) AEs during the first 7 days following each dose of vaccine.
2. Safety: To assess the frequency and severity of unsolicited AEs within 28 days of each dose of vaccine and the occurrence of any SAEs through 6 months after the last dose of vaccine
3. Immunogenicity: To measure the proportion of subjects that achieve a four-fold increase in titer, as compared to baseline, of specific serum IgG anti-COPS (S. Enteritidis or S. Typhimurium), anti-Vi (S. Typhi) polysaccharide, and anti-FliC (S. Enteritidis or S. Typhimurium) antibody at days 29 and 57, as measured by ELISA.

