7 ASSESSMENT OF SAFETY

7.1 Specification of Safety Parameters

Safety will be assessed by the frequency and severity of:

1. Solicited adverse events, reactogenicity events occurring from the time of each vaccination through 7 days after vaccination, to include:
 - a. Local injection site reactions: pain, erythema (redness), induration (swelling), and ecchymosis (bruising).
 - b. Systemic reactions: fever, chills, fatigue (tiredness), malaise (general unwell feeling), myalgia (body aches), (arthralgia (joint aches), nausea, and headache.
2. Study product-related unsolicited adverse events, non-serious adverse events occurring from the time of each vaccination through 28 days after vaccination.
3. Study product-related serious adverse events occurring from the time of the first vaccination and through the final visit (or time of early withdrawal, when applicable) for each participant.
4. New-onset chronic medical conditions occurring from the time of the first vaccination and through the final visit (or time of early withdrawal, when applicable) for each participant.

Safety assessment will also include laboratory parameters which will be evaluated at baseline (pre-vaccination) and 7 days after the first dose of vaccine and are also to include: WBC, ANC, Hg, platelet counts, creatinine, AST, ALT, TBIL, and CRP. CRP will also be evaluated at one day after receiving the first dose of vaccine (Day 2).

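### Scheduled collection of non-serious AEs can end before the 28 days that primary objective 2 requires: at 25 days after dose 1 in Cohorts A-B, and at 22 or 25 days after dose 2 in Cohorts C-D

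*Combined protocol and SAP*

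**What the plan says.** **The period.** Primary objective 2 (Section 2.3, repeated in the Synopsis) is about the "frequency and severity of unsolicited AEs within 28 days of each dose of vaccine". Section 2.2 says that "unsolicited AE reporting will occur through 28 days following the last dose of vaccine", and Section 7.1 lists "non-serious adverse events occurring from the time of each vaccination through 28 days after vaccination".

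**The visits.**
- Section 6.2 puts dose 1 on Day 1.
- Section 6.5 is a follow-up visit for Cohorts A-B and, on the same study day, "Vaccination Dose #2 (for Cohorts C and D) (Day 29 ±3"). AEs are collected there in all cohorts.
- Section 6.7 (Day 57 ±3) says: "Collection of any AEs (for Cohort C and D only) or SAEs will be recorded".
- Section 6.8 (Day 180 or 210) collects SAEs only.
- Appendix A agrees. The AE row for Cohorts A-B has no mark after Day 29. For Cohorts C-D the last AE mark is read as Day 57, while the SAE row runs on to Day 210.

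**What does not fit, or is not stated.** Section 2.2 lists Day 57 among the Cohort A-B visits and has AEs recorded at those visits, which conflicts with Section 6.7. No section says whether Day 36 and Day 57 are counted from Day 1 or from the actual dose 2. Section 5.1 has memory aids reviewed at visits 7 days after each dose, which suggests dose-based timing, but only for that visit.

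**The analysis.** Section 10.2 tabulates the percentage of participants with each AE, with an exact 95% interval. It has no rule for a participant observed for fewer than 28 days.

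**The concern.** A 28-day endpoint needs a last AE enquiry at 28 days or later. Here the closing visit is centred exactly on day 28 and may be held up to three days early. In Cohorts C-D the start of the period can also move, because dose 2 has its own ±3 window.

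Days that are not asked about count as event-free in a simple percentage. A late visit does not compensate, because events after day 28 fall outside the endpoint. The error therefore runs only towards fewer events.

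In Cohorts C-D the dose 1 period is safe, since AEs are asked about again at Days 36 and 57. Only the dose 2 period is exposed, and Section 10.1.1 gives safety with two sequential doses as the purpose of the two-dose evaluation. The Cohort C groups that receive vaccine twice have 6 and 4 participants, so one missed participant-level event moves a rate by 1/6 = 17 or 1/4 = 25 percentage points.

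**Working it through.** **Inputs.** Required period: 28 days after each dose (Sections 2.2, 2.3, 7.1). Dose 1: Day 1 (6.2). Last non-serious AE visit in Cohorts A-B, and dose 2 in Cohorts C-D: Day 29 ±3, so Days 26 to 32 (6.5). Last non-serious AE visit in Cohorts C-D: Day 57 ±3, so Days 54 to 60 (6.7). Days covered = visit day − dose day.

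**1. The plan's own figure.** On nominal days, Cohorts A-B have 29 − 1 = 28 and Cohorts C-D have 57 − 29 = 28 after dose 2. The 28 days reproduce, with nothing to spare.

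**2. Cohorts A-B.** Earliest visit: 26 − 1 = 25 days. Latest: 32 − 1 = 31 days. Three of the seven permitted days (26, 27, 28) fall short, by 3, 2 and 1 days. The worst case leaves 3/28 = 11% of the period unasked.

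**3. Cohorts C-D, Day 57 counted from Day 1** (the literal reading of the headings and of the study-day row in Appendix A). Shortest: 54 − 32 = 22 days. Longest: 60 − 26 = 34 days. The 7 × 7 = 49 permitted pairs are distributed as follows:

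| Days after dose 2 | 22 | 23 | 24 | 25 | 26 | 27 | 28 | 29 to 34 |
|---|---|---|---|---|---|---|---|---|
| Pairs | 1 | 2 | 3 | 4 | 5 | 6 | 7 | 21 |

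Pairs short of 28 days: 1 + 2 + 3 + 4 + 5 + 6 = 21 of 49. The worst case leaves 6/28 = 21% of the period unasked.

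**4. Cohorts C-D, Day 57 counted from dose 2.** 28 ± 3 gives 25 to 31 days. The worst shortfall drops to 3 days but does not vanish.

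**5. Other timings that depend on the same unstated anchor.** Counted from Day 1, the Day 36 ±1 visit falls 35 − 32 = 3 to 37 − 26 = 11 days after dose 2, and the Day 57 serum 22 to 34 days after it. Counted from dose 2, they fall at 6 to 8 and 25 to 31 days. The second set matches the post-dose-1 timing (Day 8 ±1 and Day 29 ±3).

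**6. Dose 1 in Cohorts C-D.** On the Day 1 count, the next AE visit after Day 29 is no earlier than Day 35, which is 34 days after dose 1. There is no shortfall.

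**The case against.** The strongest reply is that the reporting period is 28 days by definition, whatever the visit date. Section 7.2 requires all AEs on study to be documented, Section 6.9 allows unscheduled visits for AEs, and interim history is taken at Day 57 and at the final visit. On Section 2.2 even the Cohort A-B Day 57 visit records AEs. A reader might infer that the period itself closes early and that nothing can recover the lost days; the documents do not support that. What stands is narrower: no scheduled AE enquiry is guaranteed on or after day 28, and Sections 6.7 and 6.8 limit the later enquiries to SAEs.

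Second, the 22-day figure and the 3-to-11-day figure rest on counting from Day 1. Section 5.1 points the other way for the memory-aid visit, and a 7-day aid cannot be complete on day 3. Neither figure can be asserted as what will happen. The 25-day minimum survives either reading.

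Third, 21/49 = 43% invites the inference that about 9 of the 22 Cohort C participants will be short. That needs visit days that are uniform and independent, and the documents give no attendance data. Moreover, only 6 + 4 = 10 of the 22 receive vaccine as dose 2; the other 12 receive placebo.

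Fourth, a reader might infer bias between arms, or damage to the dose 2 reactogenicity question that Section 2 calls the main purpose of the second dose. The blinded arms within a cohort share the same windows, and solicited reactogenicity is defined over 7 days, so days 22 to 28 do not bear on it.

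Finally, the reach is limited. Cohorts A and B are past these visits, Cohort D may not be run (Synopsis), and the trial is descriptive.

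**Conclusion.** The point holds as a gap in scheduled ascertainment. The visit windows permit the last non-serious AE enquiry at 25 days after dose 1 in Cohorts A-B. In Cohorts C-D they permit it at 22 days after dose 2 (Day 1 count) or 25 days (dose 2 count). At most 3 or 6 of the 28 days go unasked. The count of 21 in 49 shows what the windows allow on the Day 1 reading and is not an expected proportion.

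The effect can only lower the unsolicited-AE rate. It does not differ between blinded arms within a cohort and does not reach SAEs. Volunteered reports and unscheduled visits may recover some events; how many cannot be judged from the documents. The conclusion rests on the AE rows of Appendix A agreeing with Sections 6.7 and 6.8, as they appear to, and not on the wider wording of Section 2.2. It is a modest defect in a primary safety endpoint, worth correcting because the correction is cheap.

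**What to change.** 1. In Sections 6.6 and 6.7 and in Appendix A (Cohorts C and D), count the Day 36 and Day 57 visits from the actual date of dose 2: 7 ± 1 and 28 ± 3 days after it. This also fits the memory-aid visit in Section 5.1 and times the post-dose-2 samples like the post-dose-1 samples.
2. Keep ±3 for the serum. For anyone seen before day 28 after dose 2, add a short phone AE query on or after day 28. Letting the visit itself run only late (for example 28 to 34 days) would close the AE gap, but it would shift the serum away from the 25 to 31 days used after dose 1.
3. Reconcile Section 2.2 with Section 6.7 and Appendix A on whether AEs are recorded at Day 57 in Cohorts A-B.
4. For Cohorts A-B, report the actual days of AE observation after the dose.

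**Cost.** Window wording and a brief call to early attenders; no extra visit or blood. One side effect: dating from dose 2 lets the Day 57 visit fall on study Days 26 + 25 = 51 to 32 + 31 = 63, so in one-dose recipients that sample would lie 50 to 62 days after dose 1, against 53 to 59 now. If that is unwelcome, the phone query alone still closes the AE gap.

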6.9 Unscheduled Visits

Unscheduled visits may be performed at the participant's request or by judgement of the PI (or designee) when necessary for the diagnosis and/or management of a finding or AEs. All unscheduled visits are to be documented.

6.10 Early Termination

A participant may withdraw from the study for any reason or the PI (or designee) may withdraw the subject for the welfare of the participant. At this visit, vital signs (oral temp, BP, and pulse) and AE recording will be completed.

7 ASSESSMENT OF SAFETY

7.1 Specification of Safety Parameters

Safety will be assessed by the frequency and severity of:

1. Solicited adverse events, reactogenicity events occurring from the time of each vaccination through 7 days after vaccination, to include:
 - a. Local injection site reactions: pain, erythema (redness), induration (swelling), and ecchymosis (bruising).
 - b. Systemic reactions: fever, chills, fatigue (tiredness), malaise (general unwell feeling), myalgia (body aches), (arthralgia (joint aches), nausea, and headache.
2. Study product-related unsolicited adverse events, non-serious adverse events occurring from the time of each vaccination through 28 days after vaccination.
3. Study product-related serious adverse events occurring from the time of the first vaccination and through the final visit (or time of early withdrawal, when applicable) for each participant.
4. New-onset chronic medical conditions occurring from the time of the first vaccination and through the final visit (or time of early withdrawal, when applicable) for each participant.

Safety assessment will also include laboratory parameters which will be evaluated at baseline (pre-vaccination) and 7 days after the first dose of vaccine and are also to include: WBC, ANC, Hg, platelet counts, creatinine, AST, ALT, TBIL, and CRP. CRP will also be evaluated at one day after receiving the first dose of vaccine (Day 2).

7.2 Methods and Timing for Assessing, Recording, and Analyzing Safety Parameters

Adverse Event (AE): ICH E6 defines an AE as any untoward medical occurrence in a patient or clinical investigation subject administered a pharmaceutical product regardless of its causal relationship to the study treatment. An AE can therefore be any unfavorable and unintended sign (including an abnormal laboratory finding), symptom, or disease temporally associated with the use of medicinal (investigational) product. The occurrence of an AE may come to the attention of study personnel during study visits and interviews of a study recipient presenting for medical care, or upon review by a study monitor.

All AEs including local and systemic reactions not meeting the criteria for "serious adverse events" should be captured on the appropriate CRF. Information to be collected includes event description, time of onset, clinician's assessment of severity, relationship to study product (assessed only by those with the training and authority to make a diagnosis, which would include MD, PA, and Nurse Practitioner, listed on the FDA Form 1572), and time of resolution/stabilization of the event. All AEs occurring while on study must be documented appropriately regardless of relationship. All AEs will be followed to adequate resolution.

Any medical condition that is present at the time that the patient is screened should be considered as baseline and not reported as an AE. However, if it deteriorates at any time during the study, it should be recorded as an AE.

Special Circumstance of COVID-19 Pandemic. While there is a U.S. Public Health Emergency for COVID-19, there is the risk of community transmission of infections. The testing of both anti-SARS-CoV-2 antibody and presence of virus by PCR on the days of vaccination (both dose #1 and #2) are intended to provide the investigators with information on potential asymptomatic or presymptomatic infections at vaccination, but the results will not be available in time prior to vaccination. Therefore, the results are intended to potentially provide alternate etiology for reactogenicity that might be observed post-vaccination which could be due to a COVID-19 infection rather than to the study product. The results of SARS-CoV-2 testing will be provided to participants at their Day 7 and Day 36 visits. If SARS-CoV-2 testing results are received prior to these visits, the research team may call participants to report these results.

Severity of Event: All AEs will be assessed by the clinician using a protocol defined grading system. For events not included in the protocol defined grading system, than the following guidelines will be used to quantify intensity.

- Mild – Grade 1: events require minimal or no treatment and do not interfere with the patient's daily activities.
- Moderate – Grade 2: events result in a low level of inconvenience or concern with the therapeutic measures. Moderate events may cause some interference with functioning.
- Severe – Grade 3: events interrupt a patient's usual daily activity and may require systemic drug therapy or other treatment. Severe events are usually incapacitating.

Changes in the severity of an AE should be documented to allow an assessment of the duration of the event at each level of intensity to be performed. Adverse events characterized as intermittent require documentation of onset and duration of each episode.

Relationship to Study Product: The clinician's assessment of an AE's relationship to Vaccine is part of the documentation process, but it is not a factor in determining what is or is not reported in the study. If there is any doubt as to whether a clinical observation is an AE, the event should be reported. All AEs must have their relationship to study product assessed using the terms: related or not related. In a clinical trial, the study product must always be suspect. To help assess, the following guidelines are used.

- Related – The event is temporally related to the administration of the study product and no other etiology explains the event.
- Not Related – The event is temporally independent of study product and/or the event appears to be explained by another etiology.

Serious Adverse Event (SAE): An adverse event or suspected adverse reaction is considered "serious" if, in the view of either the investigator or sponsor, it results in any of the following outcomes:

- Death,
- a life-threatening adverse event*,
- inpatient hospitalization or prolongation of existing hospitalization,
- a persistent or significant incapacity or substantial disruption of the ability to conduct normal life functions, or

- a congenital anomaly/birth defect.
- Important medical events that may not result in death, be life-threatening, or require hospitalizations may be considered serious when, based upon appropriate medical judgment they may jeopardize the patient or subject and may require medical or surgical intervention to prevent one of the outcomes listed in this definition. Examples of such medical events include allergic bronchospasm requiring intensive treatment in an emergency room or at home, blood dyscrasias or convulsions that do not result in inpatient hospitalization, or the development of drug dependency or drug abuse.

* *Life-threatening adverse event.* An adverse event is considered “life-threatening” if, in the view of either the investigator or sponsor, its occurrence places the patient or subject at immediate risk of death. It does not include an adverse event, had it occurred in a more severe form, might have caused death.

All SAEs will be:

- recorded on the appropriate SAE Form
- followed through resolution by a study physician
- reviewed and evaluated for intensity and causality by a physician listed on the Form FDA 1572 as the Principal Investigator or Sub-Investigator.
- reviewed by the Independent Safety Monitoring Committee and the IRB.

